3.0 Objectives / Aims

The *main objective of this proposal* is to evaluate the ability of salsalate to reduce ovarian androgen secretion, induce ovulation and decrease lipid- and glucose-stimulated inflammation independent of body composition and IR in women with PCOS; and to also improve insulin sensitivity in IR women with PCOS. Effects of salsalate will be assessed based on the following aims:

Specific Aim 1. To examine the effects of salsalate administration on the ovarian capacity to secrete androgens, menstrual function, and insulin sensitivity in PCOS.

The *hypothesis* for this aim is that salsalate treatment will decrease HCG-stimulated ovarian androgen secretion and induce ovulation in women with PCOS regardless of body composition or IR status; and may also improve insulin sensitivity in IR women with PCOS. We will test this hypothesis in a randomized double-blind placebo-controlled study. The ovarian androgen response to HCG administration will be evaluated in women with PCOS (15 lean with IR, 15 lean without IR and 15 obese) before and after administration of a therapeutic salsalate dose for ~12 weeks compared with women with PCOS receiving placebo for ~12 weeks (15 lean with IR, 15 lean without IR and 15 obese). Ovulation monitoring will occur in all subjects using timed progesterone measurements and serial follicular ultrasonography as indicated. Fractional glucose disappearance per insulin concentration unit adjusted for insulin clearance will be determined as a measure of insulin sensitivity (S_I) during a FS-IVGTT before and after salsalate or placebo administration. We anticipate that salsalate will reduce the exaggerated ovarian androgen response to HCG administration and lead to hormonal and sonographic evidence of ovulation regardless of body composition or IR status when compared with placebo. We also anticipate that salsalate will increase S_I in IR women with PCOS compared with placebo.

Specific Aim 2. To examine the effect of salsalate administration on the inflammatory response of mononuclear cells induced by lipid ingestion and glucose infusion in PCOS.

The *hypothesis* for this aim is that salsalate administration will down-regulate inflammatory signal transduction and cytokine production within MNC following lipid ingestion and glucose

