sonography within 21 days of study start reveals no evidence of follicular development in the face of a negative pregnancy test.

Visits 1 through 5 will occur during the first week of the study protocol. During Visits 1 through 4, subjects will undergo an HCG stimulation test (HCG-ST) in the CRC consisting of a single IM HCG injection during Visit 1 after documenting a negative urine pregnancy test, along with a single blood draw during all 4 visits at 0, 24, 48 and 96 hours after HCG administration to measure serum androgens and 17-hydroxyprogesterone. Visits 1 through 3 will be short lasting ~30 minutes. After one of these short visits, subjects will also undergo a body composition assessment consisting of a whole-body dual-emission X-ray absorptiometry (DEXA) scan in the Integrative Physiology Laboratory (IPL) at [name], and a magnetic resonance image of the abdomen in the Center for Magnetic Resonance Research at [name]. Visit 4 will last ~8 hours during which a cream challenge test (CCT) will also be performed in the CRC consisting of dairy cream ingestion and serial blood draws at 0, 2, 3 and 5 hours after cream ingestion to measure inflammation markers. Visit 5 will last ~7 hours and occur 2 days after the CCT during which subjects will undergo a FS-IVGTT in the CRC to assess insulin sensitivity and glucose-stimulated inflammation.

[figure not shown]
| Table 1. PRE-STUDY SCREENING | | | | |
|--|---------|---|---|---|
| STUDY PROTOCOL | WEEKS → | 0 | 4 | 8 |
| Salicylate Level | | X | X | X |
| Sex Hormone Binding Globulin | | X | | X |
| Body Composition: MRI & DEXA | | X | | |
| HCG Stimulation Test: T, A & 17OHP @ 0, 24, 48 & 96 hours. | | X | | X |
| Cream Challenge Test: MNC-derived ROS, NFκB, RNA & protein inflammat'n markers @ 0, 2, 3 & 5 hours. | | X | | X |
| Frequently Sampled Intravenous Glucose Tolerance Test: glucose, insulin, C-peptide & FFA q 1-30 minutes x 34 samples from -20-240 minutes. | | X | | X |
| Post-Study Safety Tests: CBC & CMP. | | | | X |
| Ovulation Monitoring: BBT from 0-12 weeks; P on 7th day of BBT rise; If P >2 ng/dl documented, vaginal sonography on day of & day after LH surge. | | | | |

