A predefined computer-generated randomization schedule set up by a statistician will have centralized allocation and codes secured by a research pharmacist. This schedule will be used to assign recruited subjects to receive salsalate (Amneal Pharmaceuticals, Bridgewater, NJ) 3 grams/day (lean subjects) or 4 grams/day (obese subjects) in 2 divided doses or identical placebo for ~12 weeks. Study medication will actually be administered over a range of 11 to 13 weeks to accommodate scheduling glitches without impacting any anticipated treatment effects. Subjects and study personnel will be blinded to the treatment assignment. Serum salicylate levels will be measured to assess compliance from a fasting blood sample drawn at baseline (Visit 1) and after 4 weeks (Visit 6), 8 weeks (Visit 7) and 12 weeks (Visit 8) of treatment. Compliance will be defined as salicylate levels being in the therapeutic range for rheumatology practice (10-30 mg/dl) during treatment. A Data and Safety Monitoring Board (DSMB) will keep track of salicylate levels to maintain blinding (see Section 6.0). A fasting lipid profile will also be drawn at baseline (Visit 1) and after 12 weeks (Visit 8) of treatment.

During treatment, all subjects will undergo ovulation monitoring consisting of serum progesterone measurements timed by basal body temperatures along with serial follicular ultrasonography as indicated. After the ~12 weeks of treatment, subjects will undergo repeat testing consisting of an HCG-ST during Visit 8 through 11, a CCT during Visit 11 and a FS-

IVGTT during Visit 12. Visits 8 through 12 will occur during the last week of the study protocol. See Table 1 for an overview of the study protocol and Fig. 2 for the study timeline.

Figure 2

Although it is anticipated that the majority of subjects will undergo the three main test procedures (i.e. HCG-ST, CCT and FS-IVGTT) in the order described, the order in which they will be scheduled may need to be changed to accommodate scheduling glitches, since they will be performed as outpatient procedures in accordance with the CCTS CRC operating hours. The change in order will not impact the integrity of the data.

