- **Ovulation Monitoring:** All subjects will maintain a basal body temperature (BBT) chart throughout the ~12 weeks of treatment after appropriate instructions. A blood sample (5 ml) will be drawn to measure serum progesterone to detect ovulation on the 7th day of temperature elevation of at least ¾°F from baseline indicative of a biphasic BBT response. Subjects will be instructed to alert the team regarding the potential need to schedule a progesterone measurement when 3 consecutive days of temperature elevation is evident. The length of the cycle in which a luteal range progesterone (>2 ng/ml) is documented will be used to time initiation of midcycle urine luteinizing hormone (LH) monitoring with a commercially available kit. Vaginal sonography will be performed in the CRC on the day of the color change signifying the LH surge and the following day to document follicular development and collapse, respectively, as the definitive evidence of ovulation.

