This study is not powered to compare ovulation rates among the separate groups. Thus, ovulation rate post-treatment based on detection of luteal range progesterone elevations guided by BBTs will be compared between the salsalate and placebo groups overall. Based on the inclusion criteria, patients will be anovulatory pre-treatment, thus only post-treatment rates will be compared. With a sample size of 45 in each treatment group, if we expect approximately 10% to ovulate in the placebo arm, we will have over 80% power to detect a statistically significant difference if ovulation increases by 40% in the salsalate-treated group based on Fisher's exact test with type I error set at 0.05.

Aim 2: The primary outcome for Aim 2 is lipid-stimulated NF κ B EMSA density (i.e. change from baseline). The three contrasts of interest will be comparing the mean difference in lipid-stimulated NF κ B EMSA density between the salsalate and placebo group within each study group (i.e. salsalate-treated lean IR vs placebo lean IR, salsalate-treated lean non IR vs placebo lean non IR, and salsalate-treated obese vs placebo obese). Our preliminary baseline CCT data revealed similar results in women with PCOS and obese controls.¹¹ The lipid-stimulated NF κ B EMSA density in women with PCOS (n=17) compared with lean controls (n=8) revealed a mean ($\pm SD$) % change of 20.1 ± 10.4 vs. -3.0 ± 9.1 ($p<0.0001$, ES=1.9). The secondary outcomes for Aim 2 are glucose-stimulated NF κ B EMSA density and lipid-stimulated ROS generation (i.e. change from baseline). For women with PCOS compared with lean controls, our previously published baseline OGTT data showed a mean ($\pm SD$) % change of 34.6 ± 45.7 vs. -21.6 ± 35.6 ($p<0.04$, ES=1.4),¹³ and our baseline preliminary CCT data showed a mean ($\pm SD$) % change of 92 ± 38 vs. -7 ± 22 in ROS generation ($p<0.0001$, ES=3.8). For each of these outcomes, we will use a similar GLM framework as described in Aim 1 with the same three contrasts of interest. We will use a Sidak adjustment to control the type I error for each outcome. We expect post-salsalate treatment measures in PCOS will be similar to lean controls. Based on a two-sided two-sample t-test with a 0.017 α level to account for multiple comparisons which will yield similar power to our GLM model, we will have 80% power to detect an ES ≥ 1.24 . Thus, our study is sufficiently powered for these outcome measures.

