12.3 Statistical Analysis

Initially, a full descriptive analysis of the data will be performed. Frequency distributions will be computed for all raw data and for change from baseline responses to lipid or glucose stimulation. Summary statistics will be provided by treatment group (salsalate, placebo) overall as well as by treatment group and study group (lean non-IR, lean IR, obese).

- i. Baseline data such as age, BMI, androgens, insulin sensitivity, total body fat and visceral fat will be compared between groups (salsalate: lean non-IR, lean IR, obese; placebo: lean non-IR, lean IR, obese) using analysis of variance (ANOVA) for normally distributed data or Kruskal-Wallis test for non-normal data to validate similarity of characteristics within each study group across the 2 treatment arms. If there is statistical significance, multiple comparisons between groups will be performed using a Sidak adjustment.
- ii. The primary outcome for Aim 1 is a difference in HCG-stimulated testosterone AUC between salsalate vs. placebo. To test our hypothesis, we will use a GLM framework with a dependent variable of post-treatment HCG-stimulated testosterone AUC including covariates for pre-treatment HCG-stimulated testosterone AUC, treatment indicator, study group (lean non-IR, lean IR, obese) and the treatment by study group interaction. Of primary interest will be the three contrasts of difference in mean between salsalate vs. placebo for these study groups. A Sidak adjustment will be used to control the Type I error. Analysis for the secondary measure of difference in S_i between salsalate and placebo for the insulin-resistant subjects only (lean IR, obese) will be compared using the same GLM framework, although only the overall contrast of difference in means between salsalate and placebo is of interest. Assumptions and model fit will be checked for all primary and secondary outcome analyses. Data will be transformed if necessary.

Post-treatment ovulation rates based on ultrasound documentation of follicular collapse will be compared between the salsalate-treated group and the placebo group using Fisher's exact test with type I error at 0.05. Also, ovulation rates and 95% exact confidence intervals will be estimated by study group (lean with IR, lean without IR, and obese) and treatment group.

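### Ovulation is powered on luteal progesterone (12.2) but tested on ultrasound follicular collapse (12.3), which a woman who ovulates once or late cannot meet under section 6.1; the stated power does not cover the tested endpoint, and her classification is not given

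*Combined protocol and SAP*

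**What the plan says.** Section 12.2 describes the between-arm comparison as "ovulation rate post-treatment based on detection of luteal range progesterone elevations guided by BBTs". It assumes 45 women per arm, about 10% ovulating on placebo and Fisher's exact test at 0.05, and concludes that "we will have over 80% power to detect a statistically significant difference if ovulation increases by 40% in the salsalate-treated group".

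Section 12.3, item ii, describes the same overall Fisher test at 0.05 with a different event: "Post-treatment ovulation rates based on ultrasound documentation of follicular collapse will be compared between the salsalate-treated group and the placebo group".

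Section 3.0, Specific Aim 1, expects salsalate to "lead to hormonal and sonographic evidence of ovulation regardless of body composition or IR status when compared with placebo". It does not say which kind of evidence is tested.

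The measurement procedure is in section 6.1, Ovulation Monitoring. Progesterone is drawn on day 7 of a sustained temperature rise. Then "The length of the cycle in which a luteal range progesterone (>2 ng/ml) is documented will be used to time initiation of midcycle urine" LH testing, and scans are done on the day of the LH colour change and the next day. The scans are to document "follicular development and collapse, respectively, as the definitive evidence of ovulation". Table 1 has the same gate: "If P >2 ng/dl documented, vaginal sonography on day of & day after LH surge". Section 6.0 places the monitoring within the treatment period: "During treatment, all subjects will undergo ovulation monitoring consisting of serum progesterone measurements timed by basal body temperatures", with follicular ultrasonography added as indicated.

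**The concern.** Two current sections define one comparison by two different events, and the protocol's own procedure makes those events unequal. The progesterone sample is taken after the ovulation it detects, and scanning is arranged only once that sample is positive. The ovulation that triggers scanning is therefore never the one scanned.

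Three consequences follow. The power statement belongs to an event other than the one tested. Women with a positive progesterone and no scan have no stated status: they could be counted as non-ovulators, treated as missing, or excluded. And with two definitions and no rule on file, the choice could be made after the results are seen, when it can change the answer on the same data.

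Inducing ovulation is part of the main objective in section 3.0 and of the Aim 1 hypothesis, although it is not the designated primary or secondary outcome. The primary analysis of testosterone AUC is not affected.

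**Working it through.** **Inputs from section 12.2.** 45 per arm; placebo rate about 10%; Fisher's exact test at 0.05. The test is taken as two-sided, since the plan does not say. An increase of 40% from 10% can be read as 10% + 40 points = 50%, as a salsalate rate of 40%, or as a relative rise to 10% × 1.4 = 14%.

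**Method.** With X the placebo count and Y the salsalate count, power = Σ P(X = x) · P(Y = y) over all tables (x, y) with Fisher p ≤ 0.05, where X ~ Bin(45, p₁) and Y ~ Bin(45, p₂). All 46 × 46 tables are enumerated.

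**Step 1: the plan's own figure, progesterone endpoint**

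| Reading | Rates | Power |
|---|---|---|
| +40 points | 10% vs 50% | 98.7% |
| To 40% | 10% vs 40% | 88.9% |
| Relative 40% | 10% vs 14% | 4.8% |

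The first two readings satisfy the stated figure with margin. The third does not fit. The claim is sound for progesterone, but the intended salsalate rate is unclear.

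**Step 2: who can meet each definition (sections 6.0, 6.1 and Table 1)**

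| Pattern on treatment | 12.2 (progesterone) | 12.3 (collapse) |
|---|---|---|
| No ovulation | Negative | Negative |
| One ovulation, detected | Positive | Cannot be positive: the cycle is over before scanning is arranged |
| First ovulation late, no further LH surge in the treatment period | Positive | Cannot be positive |
| Ovulation in a detected cycle and a later scanned cycle | Positive | Can be positive |

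**Step 3: power for the scan endpoint.** The documents give no rate for it. Let c be the share of progesterone-positive women who also have collapse recorded. Every value of c below is an assumption.

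*Same c in both arms; the rest counted as non-ovulators; 45 per arm kept.* The rates become 0.10c and 0.50c (or 0.40c).

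| Reading | c | Rates | Power |
|---|---|---|---|
| 10/50 | 0.59 | 5.9% vs 29.5% | 80.3% |
| 10/50 | 0.58 | 5.8% vs 29.0% | 79.4% |
| 10/40 | 0.85 | 8.5% vs 34.0% | 80.2% |
| 10/40 | 0.84 | 8.4% vs 33.6% | 79.5% |

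*Unequal c: 0.30 placebo, 0.60 salsalate.* The placebo rate is 0.10 × 0.30 = 3%. The salsalate rate is 0.50 × 0.60 = 30%, giving 94.4% power, or 0.40 × 0.60 = 24%, giving 81.4%. Capture that is higher on salsalate can therefore keep power above 80%.

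**Step 4: effect of the unstated counting rule, at c = 0.50 in both arms**

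- *Unscanned progesterone-positive women counted as non-ovulators.* 5% vs 25% gives 70.8%; 5% vs 20% gives 48.0%.
- *The same women excluded.* The placebo rate is 0.05/0.95 = 5.3%. The salsalate rate is 0.25/0.75 = 33.3% or 0.20/0.80 = 25.0%. With the arm sizes random, power is 88.8% or 67.1%.

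At this c, the counting rule alone moves power by 88.8 − 70.8 = 18.0 points or 67.1 − 48.0 = 19.1 points.

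**Step 5: unit.** The progesterone threshold that triggers the scan is in ng/dl in Table 1 and in ng/ml in section 6.1.

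**The case against.** The strongest reply has four parts.

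*Other scans may be possible.* Sections 3.0 and 6.0 allow follicular ultrasonography as indicated, and section 6.1 does not call its trigger the only one. This stands as a limit: the conclusion that such a woman cannot meet the definition applies to the procedure as written. But the phrase is undefined and no other trigger appears anywhere.

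*The classification can be inferred.* Section 6.1 treats the scan as "follicular development and collapse, respectively, as the definitive evidence of ovulation" and 12.3 uses the same event, so no recorded collapse may simply mean no ovulation. That reading is reasonable, but it is not a counting rule, and 12.2 would count the same woman as ovulating. It also does not separate a woman scanned without collapse from one never scanned.

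*No loss of power is shown.* This is correct. The progesterone calculation has margin, the capture shares are assumed, and the unequal-capture case stays above 80%. The finding is that the power is unsupported for the tested endpoint, not that the comparison is underpowered.

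*Aligning 12.2 with 12.3 would serve equally well.* It would remove the contradiction, provided the counting rule is written and power is restated. Progesterone has a gap of its own, because it is drawn only after a detected temperature rise, so a woman with a poor chart also needs a stated status.

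**Conclusion.** The concern holds. Sections 12.2 and 12.3 define one test by two events that the monitoring procedure makes unequal, and no rule classifies a progesterone-positive woman without a scan. The stated power is reproduced for progesterone (98.7% or 88.9%) and has no basis in the documents for the scan endpoint. With equal capture and unscanned women counted as non-ovulators, it carries over only if at least about 59% (10/50) or 85% (10/40) of progesterone-positive women have collapse recorded.

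The endpoint conflict and the missing rule rest on the text alone. The size of any power loss rests on assumed capture, a two-sided test and 45 evaluable women per arm. This should be fixed before analysis; it does not touch the primary outcome.

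**What to change.** 1. In 12.3, test at least one on-treatment serum progesterone above 2 ng/ml. This is the endpoint powered in 12.2, with the cutoff taken from 6.1. Say how women with no progesterone drawn are counted.
2. Report scan-confirmed collapse as a supportive analysis, and state how progesterone-positive women without a scan are counted in it.
3. If the sponsor prefers the scan as the tested endpoint, write that counting rule into 12.3 and restate power in 12.2 for the scan, giving the assumed capture.
4. In 12.2, replace the 40% increase with the intended salsalate rate and its power: about 99% for 50%, about 89% for 40%.
5. In section 3.0, say which evidence of ovulation is tested. Reconcile the progesterone unit in Table 1 with that in 6.1.

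The cost is wording and one table unit, since both measurements are already planned. The downside of the first option is that progesterone is less direct than the scan, which 6.1 regards as definitive; this is why the scan result is kept as supportive.

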4.0 Eligibility

The protocol will prospectively study healthy reproductive-age women with PCOS recruited from clinical practice or various local advertisements (see section 5.0). Volunteers interested in study participation will respond by telephone or secure e-mail (see section 5.0). They will subsequently be provided with a detailed study description and undergo an initial pre-screening using questions from an eligibility assessment form (attached). During the prescreening, volunteers will be asked to provide their name, contact information, age/date of birth, smoking status, and information about their current medical conditions, general and gynecological health status and medication use. All of the answers obtained will be documented in the eligibility assessment form which will be kept in each volunteer's study booklet. The PI will determine subject eligibility based upon the following inclusion / exclusion criteria.

4.1 General Inclusion Criteria:

- Diagnosis of PCOS based on the presence of hyperandrogenism (skin manifestations of androgen excess such as hirsutism, acne or temporal balding – or –elevation of at least one serum androgen [i.e. total testosterone, free testosterone, androstenedione or DHEA-S] using predetermined local laboratory cutoffs), oligo/amenorrhea and evidence of withdrawal bleeding after progestin administration.
- 18-40 years of age.
- Good health as evidenced by medical history, physical examination and gynecologic examination within 30 days prior to starting the study.
- Willingness to provide informed consent according to the guidelines of the University of Illinois at Chicago (UIC) Institutional Review Board (IRB).
- Willingness to use double-barrier contraception such as condoms and topical spermicide (foam, cream or gel), condom and diaphragm, diaphragm and topical spermicide or sponge with topical spermicide if sexually active. Use of a non-hormonal intrauterine device (IUD), or permanent sterilization of the subject or her partner (i.e. tubal ligation or vasectomy) is also acceptable in all instances.

4.2 General Exclusion Criteria:

- Hyperprolactinemia.
- Uncontrolled thyroid disease.
- Evidence of Cushing's syndrome, nonclassic congenital adrenal hyperplasia or a hormone producing tumor based on physical findings and serum androgen levels on initial screening.
- Known or suspected pregnancy.
- Regular vigorous physical activity during previous 6 months.

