6.0 Study Design and Procedures

This research will involve the prospective study of 90 reproductive age women (18-40 years) with PCOS using a randomized double-blind placebo-controlled study design. The randomization schedule will be stratified by body mass index (BMI) (lean: BMI ≥ 18 but ≤ 25 kg/m²; obese: BMI ≥ 30 but ≤ 40 kg/m²) and IR status study groups to ensure a balance of patients in the two study arms. IR will be defined by the insulin area under the curve from 0-120 min (insulin AUC₀₋₁₂₀) of an oral glucose tolerance test (OGTT) $> 7,000$ which is highly predictive and thus, recommended for population assessment of IR in PCOS.³⁵ Forty five (45) of the women with PCOS will receive salsalate of which 30 will be lean (15 without IR; 15 with IR) and 15 will be obese. The other 45 women with PCOS with a similar frequency distribution of BMI and IR status will receive placebo. Thus, the study will be comprised of the following 6 groups:

1. Salsalate-treated lean PCOS without IR (n=15)
 - BMI ≤ 25 kg/m² – and – 2-hour oral glucose tolerance test (OGTT) insulin area under the curve (AUC) $\leq 7,000$
2. Placebo-treated lean PCOS without IR (n=15)
 - BMI ≤ 25 kg/m² – and – 2-hour OGTT insulin AUC $\leq 7,000$
3. Salsalate-treated lean PCOS with IR (n=15)
 - BMI ≤ 25 kg/m² – and – 2-hour OGTT insulin AUC $> 7,000$
4. Placebo-treated lean PCOS with IR (n=15)
 - BMI ≤ 25 kg/m² – and – 2-hour OGTT insulin AUC $> 7,000$
5. Salsalate-treated Obese PCOS – BMI ≥ 30 kg/m² – ≤ 40 kg/m² (n=15)
6. Placebo-treated Obese PCOS – BMI ≥ 30 kg/m² – ≤ 40 kg/m² (n=15)

After the initial pre-screening, volunteers will be asked to come to the CCTS CRC at [name] for a screening visit at ~ 8:00 AM. The screening visit will occur within 1 to 4 weeks of beginning the study protocol and will last ~4 hours. At the start of the screening visit, volunteers will undergo informed consent followed by a complete history and physical, vaginal sonography, and blood draws for a hormonal evaluation if not performed previously, a complete blood count (CBC), a comprehensive metabolic panel (CMP) and an OGTT. Based on the screening results, volunteers deemed eligible for study participation will subsequently enter the study protocol beginning between days 3 and 13 following the onset of either a spontaneous or progestin-induced withdrawal bleed, or without regard to the onset of menses if vaginal

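### The pooled Fisher test for ovulation is valid but conservative and ignores the randomisation groups; a stratified exact mid-p test is a small, nearly free gain, and the anovulation premise needs reconciling with the inclusion criteria.

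*Combined protocol and SAP*

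**What the plan says.** Section 6.0 (Study Design and Procedures) states: "The randomization schedule will be stratified by body mass index (BMI", and adds IR status as the second factor. The result is three groups (lean without IR, lean with IR, obese), each planned as 15 salsalate and 15 placebo.

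Section 12.3, item ii, compares post-treatment ovulation "between the salsalate-treated group and the placebo group using Fisher's exact test with type I error at 0.05". Study group enters only descriptively, through rates and exact 95% intervals by group and arm. In the same item, the model for HCG-stimulated testosterone AUC includes study group.

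Section 12.2 (Power Analysis) says the study is not powered to compare ovulation between the separate groups and so pools them. Its inputs are 45 women per arm, roughly 10% ovulating on placebo, and Fisher's test at the 0.05 level. The effect is worded as "if ovulation increases by 40% in the salsalate-treated group". For that effect the section claims: "we will have over 80% power to detect a statistically significant difference". It disposes of baseline status as follows: "Based on the inclusion criteria, patients will be anovulatory pre-treatment, thus only post-treatment rates will be compared".

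The menstrual criterion in Section 4.1 is "oligo/amenorrhea and evidence of withdrawal bleeding after progestin administration". Section 6.0 also lets women start after a spontaneous bleed, and Section 6.1 places ovulation monitoring within the treatment period only.

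**The concern.** Inducing ovulation is part of the Aim 1 hypothesis in Section 3.0. Two features of the test work against it.

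- Fisher's test is discrete and conservative when events are few, so much of the 5% error allowance goes unused.
- Pooling discards a factor fixed by the randomisation. If ovulation rates differ between the three groups, a pooled comparison is less sensitive than one made within groups and then combined.

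The stated lack of power to compare groups justifies making one overall comparison. It does not justify an unstratified one, because a stratified test is also a single overall comparison.

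The reason given for disregarding baseline status does not follow from the criteria either. Oligomenorrhea is not anovulation, and no ovulation measurement is planned before treatment to establish it. At stake are some power for a supporting endpoint and one statement that the protocol does not bear out.

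**Working it through.** **Inputs.** 45 per arm, 10% ovulating on placebo and alpha 0.05 (Section 12.2); three groups of 15 vs 15 (Section 6.0). Sidedness is not stated, so two-sided is assumed. The documents give no ovulation rates by group, so the group rates below are assumptions.

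**Step 1: the plan's own figure.** Exact power of Fisher's test is

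Σ Bin(a; 45, p_C) · Bin(b; 45, p_T) · 1{Fisher p(a, b) ≤ 0.05}, summed over all a, b from 0 to 45.

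The 40% increase can be read in three ways:

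- 10% vs 50% (40 points added): 98.7%
- 10% vs 40% (a rise to 40%): 88.9%
- 10% vs 14% (relative increase): 4.8%

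The first two agree with the claim of more than 80% power; the relative reading does not. Fisher power first passes 80% at about 37% on salsalate (79.2% at 36%, 82.0% at 37%).

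**Step 2: true size of Fisher's test.** Setting p_C = p_T in the same sum gives about 2.0% at a 10% rate and 2.6% at 20%. Type I error is controlled, with about half the allowance unused.

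**Step 3: the stratified alternative.** Let T be the number of salsalate women who ovulate, summed over groups. Given each group's total number of ovulators m_g, the null distribution of T is the convolution of three hypergeometric distributions (15 drawn from 30, of whom m_g ovulate). The two-sided mid-p is the probability of all values less likely than the one observed, plus half the probability of those equally likely. Power comes from 20,000 simulated trials per scenario; the Monte Carlo standard error is at most √(0.5 × 0.5 / 20,000) = 0.35 points.

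On the plan's own inputs, with equal rates in the three groups:

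| Placebo vs salsalate | Fisher | Stratified mid-p | Gain (points) |
|---|---|---|---|
| 10% vs 50% | 98.7% | 99.3% | 0.6 |
| 10% vs 40% | 88.9% | 92.6% | 3.7 |

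**Step 4: where the gain comes from.** Three scenarios outside the plan's inputs, with an unstratified mid-p test added to separate the two sources:

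| Assumed rates | Fisher | Unstratified mid-p | Stratified mid-p | Total gain | Due to stratifying |
|---|---|---|---|---|---|
| 10% vs 35%, equal groups | 75.8% | 82.4% | 82.3% | 6.5 | 82.3 − 82.4 = −0.1, i.e. none |
| 2/8/20% vs 15/30/60% | 77.2% | 84.1% | 86.5% | 9.3 | 86.5 − 84.1 = 2.4 |
| 5/20/50% vs 20/45/75% | 50.7% | 56.2% | 66.0% | 15.3 | 66.0 − 56.2 = 9.8 |

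The last row has a mean placebo rate of (5 + 20 + 50)/3 = 25%, against the plan's 10%.

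**Step 5: size of the alternative.** With no treatment effect, the stratified mid-p test rejected in 3.4% to 4.7% of simulated trials, with equal or unequal group rates.

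**Step 6: the anovulation premise.** Section 12.2 takes anovulation from the inclusion criteria. Section 4.1 contains no such requirement, and monitoring in Section 6.1 begins with treatment. The premise is therefore neither required nor checked. Oligo-ovulatory women could raise the placebo rate. With salsalate held at an assumed 50% and placebo at 25%, Fisher's power is 62.5%. The stratified mid-p test gives 68.1% with equal groups, so stratifying on BMI and IR does not restore what is lost.

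**The case against.** The strongest reply is that the plan is adequate as it stands. Fisher's test is valid and conventional with only 45 × 0.10 = 4.5 expected placebo events, and it guarantees size, which mid-p does not strictly do. Power is high on the stated inputs. Ovulation is neither the Aim 1 primary outcome nor its named secondary. Group results will be shown with exact intervals. The hypothesis is an effect regardless of body composition or IR, and nothing in the documents says rates differ by group.

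Most of this stands. A reader might infer that the planned test is wrong, or that it throws away 6 points of power or more as a matter of course. The documents support neither: the larger gains need a smaller effect than planned or group rates that have to be assumed.

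A reader might also infer that women who already ovulate at entry would bias the result. They would not: allocation is randomised with concurrent controls, so the post-treatment comparison remains fair. Nor does a spontaneous bleed prove prior ovulation.

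What the reply does not answer is why a factor used in the randomisation, and in the AUC model of the same item, should be left out here when including it costs almost nothing. An effect regardless of group also does not imply equal underlying rates. Nor does it defend the anovulation sentence.

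**Conclusion.** The point holds as a modest improvement, not as a flaw that threatens the ovulation result. Fisher's test is valid, with true size of 2.0% to 2.6% at rates of 10% to 20%. On the plan's inputs the stratified mid-p test gains about 0.5 to 4 points.

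Under the assumed alternatives the gain is about 6 to 15 points. Stratification itself accounts for none of it with equal groups and about 2.5 to 10 points with unequal groups; the remainder comes from being less conservative. These figures rest on two-sided testing, 15 completers per cell and the stated group rates. They illustrate the possible gain and do not bound it.

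The statement that all patients are anovulatory before treatment conflicts with the menstrual criterion and should be corrected. That is a separate matter from the choice of test: it affects the placebo rate one may expect, does not bias the randomised comparison, and is not remedied by stratifying on BMI and IR.

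**What to change.** - In Section 12.3, item ii, replace the pooled Fisher test by a two-sided stratified exact mid-p test (Mantel-Haenszel type) over the three randomisation groups, as one overall comparison at 0.05. Report the common odds ratio with its confidence interval, and keep the descriptive rates by group and arm.
- In Section 12.2, name the same test, and state whether the 40% increase is absolute or relative.
- Reconcile the anovulation sentence in Section 12.2 with Section 4.1. If only post-treatment rates are to be compared, rest that on randomisation and on the absence of a pre-treatment ovulation measure.
- Optionally, add a sensitivity model with treatment, study group and baseline oligo- vs amenorrhea from the history already taken. It would need a penalised or exact logistic fit, because only about 4.5 placebo events are expected.

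The cost is SAP wording and negligible analysis work, with no added visit or sample. The small downside is that mid-p does not strictly guarantee size, though it stayed below 5% in every null scenario simulated.
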